11.5. Survival Follow-up

- All patients must have follow-up at ≤3-monthly intervals to confirm their survival status following the Final Study Visit unless they withdraw consent or are lost to follow-up.
- All subsequent therapies must be recorded in the eCRF if the patient has received treatment of AML following permanent discontinuation of study treatment.

12. Treatment of Subjects

BerGenBio ASA will provide bemcentinib to each study site.

Please refer to Section 14 for the procedures for preparation, storage, handling, disposal and accountability of bemcentinib.

In Part B2 cytarabine will be administered at a dose of 20 mg subcutaneously twice daily for up to 10 consecutive days repeated approximately every 28 days.

In Part B3 decitabine will be administered per standard local practice up to a maximum dose of 20 mg/m² body surface area by intravenous infusion over 1 hour, repeated daily for 5 consecutive days (i.e., a total of 5 doses per treatment cycle).

12.1. Treatment Schedule and Administration

12.1.1. Bemcentinib

In Part A, the starting dose of bemcentinib (Cohort 1) will be 200 mg on Cycle 1, Days 1, 2 and 3 (loading dose), followed by a daily maintenance dose of 100 mg.

Patients will take bemcentinib orally, fasted every day of continuous 21-day treatment cycles. Patients receiving Formulation 2 will be instructed to take bemcentinib on an empty stomach at a similar time each morning when they wake, or more than 2 hours after a light meal, with water. To maintain a fasted state, patients should be told not eat or drink anything other than water for at least 1 hour after taking the drug.

Please note that patients in Parts B2 and B3 will also take bemcentinib according to a 21-day treatment cycle i.e. the length of the bemcentinib treatment cycle will not be change to reflect the cytarabine or decitabine treatment cycle described in Section 12.1.2.

The bemcentinib dose in Part B5 (combination with low dose cytarabine) will be 400 mg orally daily for the first 3 days of treatment (loading dose) and 200 mg orally daily thereafter (maintenance dose).

Patients will record their dosing at home in a dosing diary that will be reviewed regularly by the site staff. Patients will be instructed as to the importance of following the dosing instructions they have been provided with, and for maintaining an accurate and up to date dosing record. Patients will also be instructed to bring their dosing diary and all bemcentinib

bottles, including unused and empty bottles, with them to each study visit. The site staff will record the amount of used and unused bemcentinib capsules at selected study visits.

12.1.2. Cytarabine

In Part B2 cytarabine will be administered subcutaneously according to standard practice (i.e. 20 mg/m² twice daily for 10 days followed by a rest period of \leq 1 month according to persisting myelosuppression). Cytarabine should be administered approximately 30 minutes after the bemcentinib dose.

For Part B5, cytarabine will be administered at a dose of 20 mg subcutaneously twice daily for 10 days every 28 days. Cytarabine should be administered approximately 30 minutes after the bemcentinib dose.

If toxicity presents then the cytarabine dose may be modified in accordance with the approved prescribing information or Summary of Product Characteristics (SmPC) and in accordance with local treatment guidelines.

Cytarabine is considered to be standard of care for these patients and will not be supplied or reimbursed by BerGenBio ASA.

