	
have relapsed following at least one line of therapy or be refractory to such prior therapy.
 
Part B2: Bemcentinib will be administered in combination with low dose cytarabine in patients with AML who are unsuitable for intensive chemotherapy as a result of advanced age or existing co-morbidities.
 
Cytarabine will be administered subcutaneously according to standard practice (i.e. 20 mg twice daily for 10 days followed by a rest period of \leq1 month according to persisting myelosuppression). Cytarabine should be administered approximately 30 minutes after the bemcentinib dose.
 
The bemcentinib dose to be investigated in combination will be confirmed by the SMC. If the SMC-recommended dose of bemcentinib is less than the single agent MTD, further dose escalation of bemcentinib may be considered until an MTD for the combination is identified, although the dose administered will not escalate beyond the single-agent MTD.
 
Part B3: Bemcentinib will be administered in combination with decitabine in patients with AML who are unsuitable for intensive chemotherapy as a result of advanced age or co-morbidities.
 
Decitabine will be administered at a maximum dose of 20 mg/m² body surface area by intravenous infusion, repeated daily for 5 consecutive days (i.e. a total of 5 doses per 28-day treatment cycle). The total dose per treatment cycle must not exceed 100 mg/m². Decitabine should be administered within approximately 30 minutes of the bemcentinib dose.
 
In Part B3 bemcentinib will be administered at a dose identified by the SMC in combination with decitabine. The dose of bemcentinib administered must not exceed the MTD.
 
Part B4: Single agent bemcentinib in patients with previously treated MDS (including high risk and intermediate with the exception of deletion 5q MDS). The bemcentinib dose to be investigated will be confirmed by the SMC and will be no higher than the MTD dose explored in part A.
 
Part B5: The Part B5 bemcentinib dose is based on the bemcentinib dose that was identified as safe and well tolerated in Part B2. Bemcentinib will be administered in combination with low dose cytarabine in patients with relapsed or refractory AML who have received at least

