	
one prior treatment for AML. Patients must be unsuitable for intensive chemotherapy as a result of advanced age or existing co-morbidities.
 
The bemcentinib dose will be 400 mg orally daily for the first 3 days of treatment (loading dose) and 200 mg orally daily thereafter (maintenance dose).
 
Cytarabine will be administered at a dose of 20 mg subcutaneously twice daily for 10 days every 28 days. Cytarabine should be administered approximately 30 minutes after the bemcentinib dose.

DOSE LIMITING TOXICITIES (Part A):	
DLTs will be assessed during the first 3 weeks of treatment with bemcentinib (Cycle 1), according to the National Cancer Institute (NCI) Common Terminology Criteria for Adverse Events (CTCAE) [NCI CTCAE] version 4 considered unrelated to leukemia progression or intercurrent illness, and defined as any of the following:
 
 • CTCAE Grade 3 or 4 nausea, vomiting, or diarrhea that persists despite maximum prophylactic and supportive care. • Any other CTCAE Grade 3 or 4 non-hematological toxicity that is considered to be clinically significant and causally related to bemcentinib, excluding isolated changes in laboratory results if no clinical significance or no clinical sequelae and adequately improve within 7 days. • Prolonged neutropenia with ANC <500 and platelet count <75000 after Day 42 from the start of treatment in the absence of residual leukemia • Treatment discontinuation, inability to administer one or more bemcentinib loading dose, or inability to administer three bemcentinib maintenance doses as a result of bemcentinib-related toxicity. • Any ventricular arrhythmia.
STUDY POPULATION: INCLUSION CRITERIA:	
 1. Provision of signed written informed consent 2. Histological, molecular, or cytological confirmation of: 
AML (with the exception of AML M3)
 
 • Part A: Patients with relapsed or refractory AML following treatment with cytotoxic chemotherapy or a targeted or biologic agent

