10.1. Inclusion Criteria

1. Provision of signed written informed consent
2. Histological or cytological confirmation of:

AML (with the exception of AML M3)

- a) **Part A:** Patients with relapsed or refractory AML following treatment with cytotoxic chemotherapy (with or without hematopoietic stem cell transplantation) or a targeted or biologic agent (e.g. hypomethylating agent, tyrosine kinase inhibitor, antibody)
- b) **Part B1:** Patients with AML who are unsuitable for intensive chemotherapy as a result of advanced age or co-morbidities. Patients should have relapsed following at least one line of therapy or be refractory to such prior therapy
- c) **Part B2:** Patients with diagnosed AML who are unsuitable for intensive chemotherapy as a result of advancing age or co-morbidities and who are suitable to receive treatment with cytarabine
- d) **Part B3:** Patients with AML who are unsuitable for intensive chemotherapy as a result of advancing age or co-morbidities who are suitable to receive treatment with decitabine

MDS (with the exception of deletion 5q MDS)

- e) **Part B4:** Patients with previously treated MDS (with the exception of deletion 5q MDS) including intermediate and high-risk patients who must have received prior treatment for their disease. Prior treatment may include those patients who have received hypomethylating agents, decitabine or other approved treatments for MDS.
- f) **Part B5:** Patients with relapsed or refractory AML who are unsuitable for intensive chemotherapy as a result of advanced age or co-morbidities meeting the following criteria:
 - Must have received at least one prior treatment for AML

- Are suitable to receive treatment with "low-dose" cytarabine (LDAC). LDAC is defined as 20 mg cytarabine administered subcutaneously twice daily for 10 days every 28 days.

The number of patients with refractory AML, defined as no hematological response to last AML treatment and/or patients who have received 2 or more prior treatments for AML, will be restricted to 1/3 of the sample size (i.e. no more than 6 evaluable patients). Please refer to table in Section 9.2.2.

3. Eastern Cooperative Oncology Group (ECOG) performance status 0, 1 or 2
[Appendix 1]
4. Age 18 years or older

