- q. Please refer to Section 12.1.2 for administration details.
- r. All patients that have not died prior to the Final Study Visit should be followed for survival at ≤ 3 -monthly intervals. The date of death must be reported for all patients in the eCRF (unless they are lost to follow-up or withdraw consent).

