11.3.3. Part B2, Part B3 and Part B5

Please refer to the Schedule of Events outlined in Table 6, Section 12.1.2 for cytarabine administration and Section 12.1.3 for decitabine administration.

To accommodate the dosing schedules of decitabine and cytarabine patients will need to attend the clinic / unit more frequently than required by the dosing/ assessment schedules of bemcentinib. Patients are only required to take bemcentinib capsules at clinic/ unit on those study days where study related procedures are being conducted.

In Part B2 and Part B5, bemcentinib should be administered prior to cytarabine (i.e. approximately 30 minutes) and in Part B3, decitabine should be administered within 30 minutes of the bemcentinib dose.

Please refer to the Schedule of Events outlined in Table 6. Cytarabine will be administered at a dose of 20 mg administered subcutaneously twice daily for up to ten consecutive days repeated approximately every 28 days.

Decitabine will be administered at a dose of 20 mg/m² body surface area by intravenous infusion over 1 hour repeated daily for 5 consecutive days (i.e., a total of 5 doses per treatment cycle).

11.3.3.1. Cycle 1

In addition to the assessments below, AEs and concomitant medications will be recorded on each visit. Patients will be intensively monitored throughout Day 1 to Day 4 inclusive of Cycle 1.

Visit 1 (Day 1):

- Physical examination, including weight (unless conducted as part of the screening procedures within 3 days prior to Day 1)
- BM aspirate for baseline sample for pharmacodynamic biomarker analyses (pre-dose) ONLY if the diagnostic BM aspirate was frozen (and therefore unsuitable for pharmacodynamic analyses)
- Collection of blood sample for hematology (including neutrophil and platelet count) and clinical chemistry profile (unless conducted as part of the screening procedures within 3 days prior to Day 1)
- Coagulation panel (unless conducted as part of the screening procedures within 3 days prior to Day 1)
- Routine urinalysis unless conducted as part of the screening procedures within 3 days prior to Day 1)
- Serum pregnancy test, where appropriate (unless conducted as part of the screening procedures within 3 days prior to Day 1)
- 12-lead ECGs per screening procedures (pre-dose and 2, 4, and 6 hr post-dose)

- Vital signs per screening procedures
- Collection of PK blood samples for bemcentinib and cytarabine analysis (at time-points outlined in Table 6 as appropriate)

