16.8. Safety Monitoring Committee

No formal statistical interim analyses are planned.

Data will be monitored by the SMC, in an on-going manner, to assess patient safety as outlined in Section 9.2.1.1. During Part A, the SMC will be responsible for:

- Reviewing the safety data from Cycle 1 of each dose cohort to determine whether dose escalation can proceed
- Determining the MTD prior to commencing Part B
- Defining the starting dose of bemcentinib to be administered with cytarabine/decitabine in Part B2/Part B3.

During the execution of Part B the SMC will convene after every 10 patients have completed Cycle 1 of treatment or 6 months have elapsed, whichever occurs first. Part A and Part B3 have been fully completed (i.e. last patient last visit has been achieved in both parts). Enrolment in Part B2 has been completed with a number of patients ongoing, whereas Parts B1, B4 and B5 continue to enroll as of 17 Mar 2020.

Independent Data Monitoring Committee (IDMC) has been established since 30 Oct 2019 at the request of The Federal Institute for Drugs and Medical Devices (BfArM). During execution of the remainder of Parts B1, B2, B4 and B5, patient safety data will be monitored and assessed by the IDMC in an on-going manner in accordance with the IDMC charter.

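### Part B2 cytarabine is dosed per m² in some places and as a flat 20 mg in others, and the SAP text limits cytarabine exposure and related-AE summaries to B2 although B5 also receives the drug

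*Protocol*

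**What the plan says.** **Dose in Part B2.** Protocol 12.1.2 reads "In Part B2 cytarabine will be administered subcutaneously according to standard practice (i.e. 20 mg/m² twice daily for 10 days". SAP 4.2.2 gives the same per-m² dose. Three other places in the protocol give a flat dose:

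- Synopsis, Part B2: "20 mg twice daily for 10 days followed by a rest period of" up to a month.
- Section 11.3.3, covering B2, B3 and B5: "Cytarabine will be administered at a dose of 20 mg administered subcutaneously twice daily for up to ten consecutive days".
- Opening of section 12: "In Part B2 cytarabine will be administered at a dose of 20 mg subcutaneously twice daily for up to 10 consecutive days".

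Footnote q of Table 6 tells sites "Please refer to Section 12.1.2 for administration details", and 11.3.3 points to the same section.

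**Dose in Part B5.** This is consistent. The synopsis says "Cytarabine will be administered at a dose of 20 mg subcutaneously twice daily for 10 days every 28 days", inclusion criterion 2 says "LDAC is defined as 20 mg cytarabine administered subcutaneously twice daily for 10 days every 28 days", and Protocol 12.1.2 and SAP 4.2.2 both give flat 20 mg for B5.

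**Scope of the cytarabine summaries.** Protocol 14.1.2 and SAP 4.2 state that both B2 and B5 receive low-dose cytarabine. SAP 5.6 plans the cytarabine exposure summary for B2 patients. SAP 5.8.1.1 marks the cytarabine-related AE, SAE and Grade 3 or higher entries as B2 only. SAP 4.7 mentions cytarabine for B2 alone and calls it intravenous, and SAP 5.6 uses the word infusions for days of subcutaneous dosing.

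**The concern.** On dose, the section to which sites are directed disagrees with the rest of the protocol about the basis of dosing for the same cohort. Protocol 16.8 reports "Enrolment in Part B2 has been completed with a number of patients ongoing", so the conflict bears on any B2 patient still on treatment and on how the B2 regimen is reported. SAP 5.1 pools B2 and B5 for several outputs, including ORR, AEs and QTcF. If B2 was dosed per m² and B5 at a flat 20 mg, those pooled outputs mix two cytarabine regimens. The cumulative cytarabine dose planned in SAP 5.6 would also need the dose basis stated before B2 could be read beside B5.

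On scope, the Part B primary objective (Protocol 8.1.1) covers safety and tolerability in combination with low-dose cytarabine in both B2 and B5. If a programmer follows the text of SAP 5.6 and 5.8.1.1, the larger cytarabine cohort is missing from the tables that describe how much cytarabine was given and which events were attributed to it.

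**Working it through.** The plan has no figure to reproduce here. The check compares every cytarabine dose statement and every cytarabine output, with simple arithmetic for size.

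**Step 1. Dose statements for B2**

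| Place | Dose per injection, twice daily |
|---|---|
| Protocol 12.1.2 | 20 mg/m² |
| SAP 4.2.2 | 20 mg/m² |
| Protocol synopsis | 20 mg |
| Protocol 11.3.3 | 20 mg |
| Protocol section 12, opening | 20 mg |

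The unit is not a text-extraction fault. It appears in both documents, and in each the next paragraph gives flat 20 mg for B5. The appeal to standard practice does not reconcile the statements, because the synopsis and 12.1.2 both invoke it and then give different doses.

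**Step 2. Size of the dose difference.** The documents give no body surface area (BSA), so it is an assumption. The ratio of the two doses equals BSA in m².

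- Flat dose: 20 mg × 2 per day × 10 days = 400 mg per course.
- BSA 1.6 m²: 20 × 1.6 = 32 mg per injection, 640 mg per course, ratio 1.6.
- BSA 1.8 m²: 20 × 1.8 = 36 mg, 720 mg, ratio 1.8.
- BSA 2.0 m²: 20 × 2.0 = 40 mg, 800 mg, ratio 2.0.
- Wider assumed range, 1.5 to 2.2 m²: 600 to 880 mg per course, ratio 1.5 to 2.2.

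**Step 3. Scope of the cytarabine tables**

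| Output | SAP text | SAP table title |
|---|---|---|
| Exposure, Table 14.1.8.2 | B2 (5.6) | Part B |
| Related AEs, Table 14.3.1.2.4 | B2 only (5.8.1.1) | no cohort named |
| Related SAEs, Table 14.3.1.3.4 | B2 only (5.8.1.1) | no cohort named |
| Related Grade 3 or higher AEs, Table 14.3.1.5.3 | B2 only (5.8.1.1) | no cohort named |

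SAP 5.1 names B5 as a treatment group and includes AEs among the outputs where B2 and B5 are summarised together. Its list is illustrative and does not mention exposure. The matching B3-only restriction for decitabine is correct, since B3 is the only decitabine cohort. SAP 5.14, which lists departures from the protocol's analyses, does not mention leaving B5 out.

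**Step 4. Share of patients affected.** Planned maxima are 14 for B2 and 20 for B5 (Protocol 16.9).

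- B5 among cytarabine patients: 20 / (14 + 20) = 20/34 = 59%.
- If B2 enrolled 10 to 14 and B5 10 to 20 (assumed ranges): from 10/24 = 42% to 20/30 = 67%.
- Cytarabine cohorts within Part B: (14 + 20) / (4 × 14 + 20) = 34/76 = 45%.

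**The case against.** The case for treating this as minor clean-up is reasonable.

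- B2 enrolment had closed, and the number of B2 patients continuing under this protocol version is not stated. Cytarabine is a non-IMP given as standard of care, with modification allowed under the label and local guidelines. Actual doses are logged (Protocol 14.1.2.2) and listed (Listings 16.2.5.2 and 16.2.5.5). No response definition, test or sample-size input uses the cytarabine dose. The dose carried from B2 to B5 is that of bemcentinib, according to the synopsis. All of this stands, and it limits the dose issue to any continuing B2 patients and to correct reporting.
- The table titles and SAP 5.1 favour including B5, and the table shells are not among the documents. Omission is therefore not shown. Even on the restrictive reading, B5 events stay in the all-cause tables, the bemcentinib-related tables and the listings. This also stands, but it does not remove the conflict: the B2-only tags are explicit, and a programmer could defend either reading.
- The primary objective concerns the safety of bemcentinib in combination, and the protocol does not ask for cytarabine-attributed tables. That is fair. But the SAP chose to produce them, and they should then cover everyone who received the drug.
- SAP 5.1 already plans separate B2 and B5 groups, and a protocol dose correction is an amendment. Both points are right and are reflected in the fix.

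**Conclusion.** Both parts hold. The B2 cytarabine dose is stated on two bases that differ by a factor of 1.6 to 2.0 at an assumed BSA of 1.6 to 2.0 m², and the higher one sits in the section to which sites are referred. The text of SAP 5.6 and 5.8.1.1, read as written, leaves up to 20 of 34 cytarabine patients out of four tables, while other parts of the SAP imply that they are included. The primary safety objective would still be served by the all-cause and bemcentinib-related tables, and no efficacy inference depends on either point. Two things cannot be settled from the documents: which dose B2 patients actually received, and which reading the table shells follow. This should be fixed. The wordings slip in SAP 4.7 (route, and B5 omitted) and SAP 5.6 (infusions) are minor and can be corrected at the same time.

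**What to change.** Make two checks first:

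1. Establish the B2 dose basis from the dosing records and from section 12.1 of each of the four country protocols that the SAP covers.
2. Establish whether the eCRF records relationship to cytarabine in B5. Protocol 15.3.2 asks for causality to the IMP only, whereas Listing 16.2.7.4 implies that cytarabine causality is collected. The eCRF is not among the documents.

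Then change the text:

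- **Dose:** state the confirmed B2 regimen identically in the synopsis, Protocol 11.3.3, the opening of section 12, Protocol 12.1.2 and SAP 4.2.2, noting any country difference.
- **SAP 4.7:** name both B2 and B5 as receiving cytarabine, by the subcutaneous route.
- **SAP 5.6:** summarise cytarabine for B2 and B5 by cohort, as cycles started, days administered and total cumulative dose.
- **SAP 5.8.1.1:** change the scope of the three cytarabine entries to Parts B2 and B5, by cohort.
- **Pooling:** keep the separate B2 and B5 columns beside any pooled B2 and B5 column in these tables.
- **If B5 attribution to cytarabine was not collected:** say so in the SAP, in 5.14 or beside the affected entries.

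No new procedures or data are needed. The SAP edits are wording and table scope. The protocol edit has to be submitted as an amendment under Protocol 18.8, possibly in more than one country version.

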12.1.3. Decitabine

In Part B3 decitabine (Dacogen[®]) will be administered per standard local practice up to a maximum dose of 20 mg/m² body surface area by intravenous infusion over 1 hour, repeated daily for 5 consecutive days (i.e., a total of 5 doses per treatment cycle). The total daily dose must not exceed 20 mg/m² and the total dose per treatment cycle must not exceed 100 mg/m². The cycle should be repeated every 4 weeks depending on the patient's clinical response and observed toxicity. It is recommended that patients be treated for a minimum of 4 cycles; however, a complete or partial remission may take longer than 4 cycles to be obtained. Treatment may be continued as long as the patient shows response, continues to benefit or exhibits stable disease, i.e., in the absence of overt progression, in accordance with local treatment practice. Decitabine is considered to be standard of care for these patients and will not be supplied or reimbursed by BerGenBio ASA.

12.2. Dose Modification

12.2.1. Bemcentinib

If a patient experiences drug-related toxicity which requires treatment with bemcentinib to be interrupted, a delay of up to 14 days is permitted to allow for resolution of toxicity. Toxicities must have resolved to Grade ≤ 1 or to baseline for treatment to recommence. For Grade 1 or Grade 2 (tolerable) toxicity, the patient may resume dosing at the same dose level. For \geq Grade 2 (intolerable) toxicity, the patient may resume dosing at a dose level defined by the grade of the toxicity and the number of occurrence(s) of prior toxicity as outlined in Table 7. A maximum of two dose reductions are permitted.

Table 7: Dose Modification of Bemcentinib Daily Dose for Toxicity

Grade (CTCAE)	Recommended Dose Modification
Grade 1 and Grade 2 (tolerable)	
Any occurrence	Maintain dose if toxicity is tolerated by the patient
Grade 2 (intolerable)	
1 st or 2 nd occurrence of same adverse event	Interrupt treatment until toxicity returns to baseline, Grade 1 or tolerable Grade 2 Resume dosing at same dose
3 rd occurrence of same adverse event	Interrupt treatment until toxicity returns to baseline, Grade 1 or tolerable Grade 2 Dose reduce by 100 mg
4th occurrence of same adverse event	Discontinue permanently
Grade 3	
1 st occurrence	Interrupt treatment until toxicity returns to baseline, Grade 1 or tolerable Grade 2 Dose reduce by 100 mg or Discontinue permanently if dose has already been reduced
2 nd occurrence of same adverse event at G3	Discontinue permanently
Grade 4	
1 st occurrence	Discontinue permanently
Notes:	

• Treatment interruption for bemcentinib-related toxicity should be limited to 14 days• Dose reduction below 100 mg daily is not possible (a single capsule contains 100 mg bemcentinib)• Patients being considered for dose reduction or permanent discontinuation of bemcentinib, should be discussed with the Medical Monitor	

If after a 14-day delay, toxicity has not resolved to Grade ≤ 1 or to baseline the patient should be withdrawn from the study.

In clinical study BGBC001 bemcentinib exhibited evidence of exposure-related QTc prolongation, and it is anticipated that QTc prolongation could be dose-limiting in this study. In order to reduce the risk of QTc prolongation, all efforts should be made to maintain the patient's serum potassium levels at >4 mmol/L during treatment with bemcentinib and for 2 weeks following completion of therapy. Serum calcium and magnesium should be measured and reasonable efforts made to maintain at normal levels throughout treatment. Patients with a QTc of ≥ 480 ms should be closely monitored on the clinical trial unit until their QTc falls below 480 ms and their electrolytes should be measured and corrected as necessary.

If a patient experiences QTc prolongation despite normal serum potassium and magnesium levels, bemcentinib dosing should be modified as outlined in Table 8. All values refer to the mean of triplicate serial ECG recordings. If a patient experiences a ventricular arrhythmia at any time, they should be withdrawn from the study.

Table 8: Dose Modification of Bemcentinib Daily Dose for QTc Prolongation

QTcF	Recommended Bemcentinib Dose Modification
Grade 1 (451-480 ms)	
Any occurrence	No dose modification required
Grade 2 (481-500 ms)	
1 st occurrence	Continue dosing and conduct weekly ECGs; i) if QTcF reduces to \leq Grade 1 by 14 days from initial recording, no dose modification is required ii) if QTcF does not reduce to \leq Grade 1 by 14 days from initial recording, dose reduce by 100 mg
\geq 2 nd occurrence (without dose modification)	Repeat procedure for "1 st occurrence"
\geq 2 nd occurrence (at reduced dose)	Continue dosing and conduct weekly ECGs; i) if QTcF reduces to \leq Grade 1 by 14 days from initial recording, no further dose modification is required ii) if QTcF does not reduce to \leq Grade 1 by 14 days from initial recording, interrupt treatment for \leq 14 days - if QTcF reduces to \leq Grade 1, no dose modification is required and dosing can recommence; if treatment interruption is required on more than 2 occasions at reduced dose, dose reduce by another 100 mg or discontinue treatment if dose reduction is not possible - if QTcF does not reduce to \leq Grade 1, dose reduce by another 100 mg or discontinue treatment if dose reduction is not possible

>Grade 3 (\geq501 ms)	
1 st occurrence	Interrupt treatment for \leq 14 days; i) if QTcF reduces to \leq Grade 1, dose reduce by 100 mg or discontinue treatment if dose reduction is not possible ii) if QTcF does not reduce to \leq Grade 1, discontinue treatment
2 nd occurrence	Discontinue permanently
Ventricular arrhythmia	
1 st occurrence	Discontinue permanently
Notes:	

 Serum calcium, magnesium and potassium should be measured regularly whilst receiving bemcentinib; all abnormal results should be corrected; check for use of concomitant medication that are associated with QT prolongation. The mean QTcF value from triplicate ECG readings should be used when considering dose modification Treatment interruption for bemcentinib-related toxicity should be limited to 14 days Dose reduction below 100 mg daily is not possible (a single capsule contains 100 mg bemcentinib) Patients being considered for dose reduction or permanent discontinuation of bemcentinib should be discussed with the Medical Monitor 	

